## **CBCL** assessments in the **TEDDY** protocol

The parent (primary caretaker) should complete the CBCL on an annual basis when the child is 3.5, 4.5 and 5.5 years of age. The CBCL should be completed by the parent at home.

Due to restrictions from the scale constructor the Pervasive Developmental Problems Scale of the CBCL will be administered as well. This scale might show psychological problems not classified as internalizing or externalizing.

It is important that each site has prepared a plan for referral or counselling of children who score high on any of the scales.

## 8.12.4.7. Identifying Family Characteristics that Discriminate Study Completers from Study Drop-Outs

To improve study efficiency and participant retention, it will be important to identify family characteristics predictive of study completion and drop out. Both demographic and psychosocial measures will be assessed for this purpose. These data will be collected by questionnaire or other study procedures, as described previously.

**Demographic predictors.** Likely candidates for demographic predictors of study retention and drop out include: family history of diabetes; convenience to the study site (including travel distance and time); expenses associated with study visits; availability of transportation to study visits; parental employment and whether work must be missed for study visits; extent of other child-care or family-care demands; child birth order; child gender; parental age, parental

education, parental income; single-parent status, child and parent race, and study site.

**Psychosocial predictors.** Likely candidates for psychosocial predictors of retention and drop-out include: parental anxiety and diabetes worry in response to the child's at-risk status (with high anxiety and diabetes worry associated with study retention); parental beliefs about the likelihood the child will develop diabetes (with parental beliefs that the child will never develop diabetes associated with drop-out); parental depression (with high depression more likely to be associated with drop out); negative life events in the parent or child (high number associated with drop-out); parental concerns with confidentiality or possible loss of medical insurance (higher concern associated with drop-out); parental satisfaction (low satisfaction associated with drop-out). Certainly the relative contribution of father vs. mother assessments on these variables is of interest, and may differ across cultures. Once the child reaches the age of assent, child variables may become predictive of study retention or drop-out.

## 8.12.5. Self-assessment pubertal status instruments

Many children progress to type 1 diabetes (T1D) during puberty but little is known about the potential effects of puberty on autoantibody seroconversion. The TEDDY cohort provides a unique opportunity to prospectively follow children with known genetic risk for T1D through the development of puberty in order to definitively answer questions regarding the effects of androgens and estrogens on diabetes risk.

**Specific Aim**: To determine if pubertal progression is associated with augmentation in risk for autoantibody seroconversion or development of T1D amongst children in the TEDDY cohort.

**Hypothesis 1**: Initiation of puberty is associated with an increased risk of seroconversion from negative to positive.

**Hypothesis 2:** Initiation of puberty is associated with an increased risk of transitioning from single antibody to multiple antibody positivity.

**Hypothesis 3:** Initiation of puberty is associated with an increased risk of developing T1D.

Therefore TEDDY will use self-assessment pubertal status instruments every 6 months for TEDDY visits beginning at age 8 years and until pubertal status is assessed as Stage 5 for both pubic hair and breast development/genitalia or the child reaches 15 years of age. Self-assessment may be done at the TEDDY clinic during the visit or at home before the visit. The self-assessment can be made by the parent or by the child.

## 8.13. Specimen and data collection between clinic visits

## 8.13.1. Stool

Stool specimens will be collected monthly by the family in the period between clinic visits; monthly stool collection will occur up until 48 months of age, every three months until 10 years of age and then biannually thereafter. In August 2018 all stool sample collections were stopped on all subjects. Stool sample collection compliance was less than 20% in Europe and 15% in the US. The small numbers did not warrant the cost of collection, processing, nor the burden on the families. Stool will be collected and shipped as described above. (Section 8.4)

## 8.14. Specimen testing

Islet cell autoantibodies will be assayed as specimens are obtained to determine whether a subject has reached the study's primary endpoint (see Section 9.1). Metabolic testing will be performed as described in Section 8.15.to diagnose diabetes in subjects who are persistently autoantibody-positive. The remaining testing will be performed on a case-control basis. For case subjects, all specimens obtained prior to the subject reaching the study's primary or secondary endpoints will be tested as described below and in Table 3. Control subjects will be matched to cases as described in Section 10.5.2. The testing procedures described below reflect the current state of knowledge and technology. As new hypotheses are developed and improved methodologies become available, they will be incorporated into the study to the extent possible.

### 8.14.1. Autoantibodies

## 8.14.1.1. Background

Autoantibodies against islet antigens are markers of T1DM. Autoantibodies that have been repeatedly shown to be markers of T1DM are islet cell antibodies and the biochemically defined antibodies against insulin, glutamic acid decarboxylase antibodies (GADA) and IAA or IA-2A. The biochemically defined antibodies to GADA, IA-2A, and to IAA will be measured as outcome markers in the TEDDY study. Antibodies will be measured on samples obtained from each scheduled clinic visit. ZnT8A will also be measured on samples that are found to be positive for at least one of the three islet autoantibodies (GADA, IA-2A and/or IAA), on all future samples of subjects who have had ZnT8A measured on any past sample (unless subject becomes antibody negative for all antibodies for one year – at which point ZnT8A would be stopped until autoantibody positivity reappears for GADA, IA-2A and/or IAA) and on samples of subjects who are deemed persistent confirmed single or multiple autoantibody positive.

## 8.14.1.2. Reference Laboratories

Measurements will be performed in two central laboratories, one located in the US and another in Europe. The US central laboratory will measure samples from Washington State, Florida/Georgia, and Colorado clinical centers, and the European central laboratory will measure samples from Finland, Germany and Sweden clinical centers. All samples identified as positive and a subset of negative samples will be tested in both central laboratories. Autoantibodies in samples will be classified as positive only if reported positive in both central laboratories.

Note: ZnT8A measurement will only be performed at the US central laboratory and the lab will perform the measurements for both the US and European sites.

## 8.14.1.3. Sampling

Two aliquots of 200  $\mu$ L each of serum will be obtained every three months for the first four years of life at each clinic visit for determination of autoantibodies. At 4 years of age and beyond those children who have been deemed persistent autoantibody positive will continue to have two aliquots of 200  $\mu$ L each of serum collected every three months for determination of autoantibodies while all other subjects will have two aliquots of 200  $\mu$ L each of serum collected every six months for determination of autoantibodies. One of the samples will be sent to the Autoantibody Reference Laboratory for testing, and the other sample will be sent to the NIDDK repository for storage.

A single aliquot of sample will be utilized by the reference laboratory to determine GADA, IAA, IA-2A autoantibodies and ZnT8A on samples that are found to be positive for at least one of the three islet autoantibodies (GADA, IA-2A and/or IAA), on all future samples of subjects who have had ZnT8A measured on any past sample (unless subject becomes antibody negative for all antibodies for one year – at which point ZnT8A would be stopped until autoantibody positivity reappears for GADA, IA-2A and/or IAA) and on samples of subjects who are deemed persistent confirmed single or multiple autoantibody positive. It is envisioned that the reference laboratory will repeat all positive samples internally prior to reporting positive or negative, and will measure twice, if specific autoantibodies positive are confirmed, and up to three determinations if there is discrepancy between initial positive and second determination (2/3 internal lab reported as positive, with mean of)consensus positives or negatives reported in WHO units). Results will then be sent electronically to the Data Coordinating Center. The Data Coordinating Center will then send the NIDDK repository the ID for all positive samples and a subset of negative samples (5%), and the repository will send the second aliquot of serum to the alternate Reference laboratory for confirmatory testing.

## 8.14.2. Infectious Agents

## 8.14.2.1. Background

Viral infections during pregnancy and childhood have been associated with increased risk of T1DM in both human and animal studies. The most well known example is congenital rubella, which seems to lead to diabetes in 10-20 % of infected individuals (Hyöty and Taylor, 2002). Routine immunizations have greatly decreased the number of rubella virus infections making it difficult to evaluate this question in TEDDY.

Currently the strongest candidate for diabetogenic viruses is the group of enteroviruses. These viruses consist of more than 60 different serotypes and are common in all age groups, particularly in young children, who experience several serial infections by different serotypes. Enterovirus infections have been linked to T1DM in several cross-sectional case-control studies during the past 30 years (Graves et al., 1997; Hyöty and Taylor, 2002; Hyöty 2002). Certain virus strains can also cause diabetes in mice and damage beta cells in vitro. In addition, their risk effect has been documented in many prospective studies suggesting that enterovirus infections could play a role in the initiation of the process. However, these prospective studies have been based on relatively small series, and no association was found in two of them. Accordingly, there is a clear need to confirm the risk effect of enterovirus infections in larger prospective series using standardized protocols and methods.

Several other viruses have also been connected to the pathogenesis of T1DM, even though the evidence is less convincing than that for enteroviruses. Among the most interesting candidates are rotaviruses, which have been linked to T1DM in a previous prospective study (Honeyman et al., 2000). However, another prospective study failed to show any risk effect (Blomqvist et al., 2002). Rotavirus can also infect beta cells in vitro (Coulson et al., 2002) and share mimicry epitopes with beta cell autoantigens (Honeyman et al., 1998). Other potentially interesting viruses include cytomegalovirus, mumps virus, parvovirus and retroviruses (Hyöty and Taylor, 2002). Practically nothing is known about possible role of other microbes, such as bacterial infections and intestinal microbiota.

Due to the large amount of potentially interesting microbes TEDDY will first focus on the two most likely candidates, enteroviruses and rotaviruses (Tier 1 agents), but leaving open all options to evaluate the role of any other agents. Therefore, a wide range of samples, including plasma, stool and nasal swab samples, will be collected for a long-term storage in a way, which allows the screening of a wide range of microbial agents.

#### Diagnosis of Tier 1 agents

Diagnosis of enterovirus infections in prospective studies is more demanding than that of many other virus infections. A great majority of infections (90%) are subclinical and diagnosis is based on the detection of the virus (virus isolation) or viral nucleic acids (RT-PCR) in clinical samples or on the measurement of enterovirus-specific antibodies in serum. The sensitivity of these methods depends on technical performance of the assay as well as the timing of sampling (acute vs. convalescent sample) and the test's ability to detect all enterovirus serotypes.

Current RT-PCR assays can detect practically all enterovirus serotypes, but the virus is detectable only during a limited period following the infection, usually from some days up to two weeks in blood and up to 2-6 weeks in stools. Antibodies can be detected longer after the infection, and in prospective studies significant increases in IgG, IgM or IgA class antibodies between serial samples can be used to diagnose infection. However, the sensitivity of antibody assays is not very good, mainly because the large number of enterovirus serotypes makes it difficult to cover them all.

[figure not shown]
In the TEDDY study serial samples will be collected on a regular basis during the follow-up and the length of sample intervals greatly influences the sensitivity to detect enterovirus infections. The investigators of the TEDDY consortium have a long experience from the diagnosis of entrovirus infections in prospective series, and the decision to keep the sample intervals relatively short (monthly) is based on this experience.

For example, in the Finnish DIPP study, where serum samples have been collected every 3-6 months and stool samples every month, altogether 5.7 % of the follow-up serum samples from the case subjects (children who developed clinical diabetes) and 2.2 % of serum samples from control subjects were positive for enterovirus RNA (unpublished findings). The corresponding figures for stool samples were 9.4 vs. 7.9 %, respectively (Salminen et al., 2004). In most cases the child was enterovirus positive in serum only once during the follow-up while the virus was often detected repeatedly in stools as the child experienced serial infections. However, only a single stool sample was usually positive during each infectious episode, even though in some cases the same virus was detected in two consecutive samples taken one month apart.

## 8.14.2.2. Serology for infectious agents

A 100  $\mu$ L aliquot of plasma will be used for enterovirus and rotavirus serology. Specific antibodies will be measured by ELISA. Specific methods will be determined by the testing laboratories once they are chosen by NIH. Additional aliquots of plasma will be stored at  $-70^{\circ}$ C to allow for future testing for other infectious agents.

# 8.14.3. Serum Cytokines/Inflammation Markers

Serum proteins that are markers of inflammation or that can distinguish infection or inflammation 'type' will be considered for measurement on a case-control basis. These include CRP measured with highly sensitive assays, and cytokines and chemokines that are relatively stable (i.e. can be measured in blood samples kept at room temperature for up to 24 hours). The steering and appropriate advisory committees will select the markers to be measured. One aliquot of 100

 $\mu L$  of serum will be obtained for the TEDDY study for measurement of inflammatory markers.

## 8.14.4. Tissue Transglutaminase antibodies

T1DM and celiac disease share HLA susceptibility alleles. Tissue transglutaminase antibodies are markers of celiac disease and are a result of an abnormal immune response to dietary gluten. Diabetes-associated autoimmunity may also be influenced by dietary gluten intake. The TEDDY study cohort therefore provides an opportunity to investigate the environmental determinants of celiac disease and determine whether an abnormal response to gluten in the form of tissue transglutaminase antibodies modifies T1DM risk. Measurement will be performed on all subjects at age 2 years and annually thereafter. This will be performed on serum aliquots used for islet autoantibody measurements; the islet antibody sample blood volume will be increased to 220 µl. The measurements of the transglutaminase antibodies samples will be performed in the two Autoantibody Reference Laboratories. If the annual transglutaminase antibodies sample, which starts at 2-years, is positive, the antibodies are analyzed again after 3 months (if subject is on 6 month visit schedule, the antibodies are analyzed again after 6 months); if negative the antibodies are analyzed again after one year. If confirmed positive, the child will have attained the TEDDY study endpoint for transglutaminase antibodies. Children positive and those negative for transglutaminase antibodies will continue to be screened annually. Persistently positive children will be referred to their pediatricians for confirmation of CD diagnosis outside of the study protocol by an intestinal biopsy and possible initiation of gluten free diet, if clinically indicated. These aliquots will be stored by the central laboratories at  $-20^{\circ}$ C for the duration of the study.

## 8.14.5. Thyroid autoantibodies and TSH

Thyroid disease is common in children diagnosed with type 1 diabetes (De Block et al, 2001). In the Swedish BDD study, 12 % of newly diagnosed children were positive for TPOA and or ThGA (Jonsdottir et al, 2013). Similarly, in newly diagnosed type 1 diabetes (T1D) children in the DAISY study almost 25% had TPOA (Triolo et al, 2011). In children to parents with T1D followed in the BABYDIAB study, TPOA showed an accumulated risk of 20% by 14 years of age and occurred more often in GADA positive children ([name] et al, 2009). Cross-sectional preliminary data from children at genetic risk for T1D without family history of diabetes, followed prospectively in the DiPiS study, revealed that 6 % were positive for TPOA and 10 % for ThGA at 10 years of age (analyses are ongoing). Additionally, preliminary data from children with multiple islet autoantibodies including GADA, indicated that 14 % have persistent autoimmunity for thyroid disease, some developing thyroid autoimmunity already at age 5 or 6. Autoantibodies against TPO are found in 2-5% of the general population, although this prevalence is greater with increasing age, and less in children. HLA DR3 is related to both thyroid and islet autoimmunity, and in islet

autoimmunity especially to GADA. Additionally, polymorphisms at other non-HLA loci such as CTLA4 are known to influence both T1D and thyroid disease (Ueda et al, 2003). Although thyroid disease is common among newly diagnosed type 1 diabetes patients, it is important to determine the relationship between early thyroid autoimmunity and islet autoimmunity, their temporal relationship, and genetic influences on these.

Hypotheses:

- 1. Incidence of Islet and thyroid autoantibodies are statistically related in individuals in the TEDDY cohort.
- 2. The increased co-occurance of GADA and thyroid autoantibodies is not explained solely by the presence of the HLA DR3 haplotype.
- 3. The increased co-occurance of islet and thyroid autoantibodies is not explained solely by non-HLA loci known to be associated with both T1D and thyroid disease.
- 4. Islet antibodies precede thyroid antibodies in individuals in the TEDDY cohort.

TEDDY will test autoantibodies to thyroid peroxidase (TPOA) and thyroglobulin (ThGA):

- In all children at 8 years of age or at current visit for those older than age 8. Samples from children positive for either thyroid antibody will also be tested for TSH in the same sample.
- 2. In all children at 14 years of age. Samples from children positive for either thyroid antibody will also be tested for TSH in the same sample.
- 3. Children positive for TPOA and/or ThGA at the 8 year visit and/or the 14 year visit will have a confirmatory sample draw at the next TEDDY visit, which will be analysed for TPOA and ThGA.
- 4. In children positive for either thyroid autoantibody at a given sample from step 1 or step 2, additional samples previously collected on that individual will be tested for TPO and ThGA autoantibodies sequentially backwards in sampling age to determine the first sample with either thyroid autoantibody.
- 5. All TEDDY children who have developed diabetes should be analysed for TPO and ThGA autoantibodies at the time of clinical diagnosis or at the last TEDDY visit prior to diagnosis.

Children who are found to have thyroid autoimmunity with or without elevated TSH will be informed by TEDDY staff and will be referred for medical care outside of TEDDY based on the normal site-specific protocol.

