This final visit will be the "official" end-point for the child's participation in the TEDDY Study and will offer an opportunity for psychological support to the family.

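### Thyroid back-testing omits children first found positive at diabetes diagnosis, so the islet–thyroid order is not identified for them, mainly those diagnosed before age 8

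*Protocol*

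**What the plan says.** Section 8.14.5 lists four hypotheses on thyroid autoimmunity. The fourth is "Islet antibodies precede thyroid antibodies in individuals in the TEDDY cohort".

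The testing plan has five steps:

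- Step 1 tests thyroid antibodies "In all children at 8 years of age or at current visit for those older than age 8".
- Step 2 tests "In all children at 14 years of age".
- Step 3 adds a confirmatory draw for positives at the 8- and 14-year visits.
- Step 4 goes back through the stored samples: "In children positive for either thyroid autoantibody at a given sample from step 1 or step 2, additional samples previously collected on that individual" are to be tested "sequentially backwards in sampling age to determine the first sample with either thyroid autoantibody".
- Step 5 says "All TEDDY children who have developed diabetes should be analysed for TPO and ThGA autoantibodies at the time of clinical diagnosis", or else at the last visit before it. No backward testing is attached to this step.

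Two other sections matter. Section 9.2.1 makes the post-diagnosis visit the official "end-point for the child's participation in the TEDDY Study". On islet antibodies, section 8.14.1.1 says "Antibodies will be measured on samples obtained from each scheduled clinic visit", so islet onset is dated prospectively from infancy.

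**The concern.** A comparison of which antibody came first needs an onset date for both. The islet date comes from serial testing in every child. The thyroid date comes from step 4, which is triggered only by a positive at step 1 or step 2. A child who develops diabetes before age 8 reaches neither, and the only thyroid result is the step 5 sample. That sample shows that thyroid antibodies were present by diagnosis, not when they appeared.

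The missing information is not missing at random with respect to the question. It is missing in children whose islet disease moved fastest, at a moment when islet antibodies have usually been present for some time. What is at stake is the order asked about in hypothesis 4 and, to a lesser degree, the timing of thyroid onset in hypothesis 1, which relates the incidence of the two kinds of antibody.

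**Working it through.** **1. Which children reach backward testing (section 8.14.5 with section 9.2.1).**

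- Thyroid-positive at 8 or 14, diabetes later: back-tested under step 4. No gap.
- Negative at 8, positive at a later diagnosis: thyroid onset is bracketed between the two samples. If islet antibodies appeared before 8, islet-first is supported by data, subject to transient thyroid positivity. If both antibodies arose inside that interval, the order is unknown.
- Diagnosed before 8, positive at step 5: no earlier thyroid test, no backward test and no later visit. The order is unknown.

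**2. What follows if the step 5 sample is taken as thyroid onset.** A child is scored islet-first whenever the first islet-positive sample precedes the step 5 sample. Section 2 says islet autoantibodies precede overt diabetes in most cases, so the score hardly depends on the true thyroid onset. A small simulation illustrates this. Diagnosis age was uniform from 2 to 8 years, both onsets fell between 0.5 years and diagnosis, and the true islet-first share was set in advance:

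| True islet-first share | Scored islet-first using the step 5 date |
|---|---|
| 30% | 100% |
| 50% | 100% |
| 70% | 100% |

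**3. Rough number of children affected.** The protocol gives no figure for this, so the count is built from its other figures.

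- Enrolment and diabetes by age 15 (section 10.3): 7,013 general population at 4% and 788 relatives at 13.3%, tabulated as 281 + 105 = 386. Section 9.2 says up to 380.
- Shape of onset (section 10.2.3): exponential, so F(t) = 1 − (1 − F15)^(t/15). With F15 = 4% this gives 1.35% at 5 years and 2.68% at 10 years, matching the protocol's 1.4% and 2.7%.
- Before age 8, general population: 1 − 0.96^(8/15) = 2.15%, about 151 of 7,013.
- Before age 8, relatives: 1 − 0.867^(8/15) = 7.33%, about 58 of 788.
- Together about 209 of 386, or 54%. Scaled to 380 cases, about 206.
- Thyroid positivity in newly diagnosed children (section 8.14.5): 12% in one cited study and almost 25% in another. 206 × 0.12 = 24.7 and 209 × 0.25 = 52.3.

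This gives up to about 25 to 52 children diagnosed before 8 with a thyroid-positive step 5 sample and no dating. Children whose two antibodies both arise between the age-8 test and diagnosis would be added, but the protocol gives no basis for counting them.

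**The case against.** A reader might infer that every child tested at diagnosis is scored islet-first and that hypothesis 4 is therefore favoured by design. The protocol does not support that. It gives no rule for dating or scoring step 5 positives, and such a rule could properly sit in a statistical analysis plan that is not at hand. The bias arises only if the step 5 date is used as onset. Children positive at 8 or 14 are already back-dated, many later diagnoses have a bracketed onset, and section 9.2 allows for diabetes without an identifiable islet-positive period.

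A reader might also extend the point to hypotheses 2 and 3. As worded, these concern whether co-occurrence is explained by HLA DR3 or by other loci, and step 5 still records whether thyroid antibodies are present. Nor can the gap be turned into a p-value, because the protocol gives neither the number of other doubly positive children nor a test for the order.

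The count is open to challenge. The 12% and 25% are not broken down by age, and section 8.14.5 says thyroid peroxidase antibodies become more common with age in the general population. Sections 8.11 and 8.12.1.2 mention higher diabetes incidence around ages 10 to 15, which could lower the 54% share. Finally, the thyroid hypotheses are not among those in section 5, and neither primary outcome is affected.

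All of this stands and limits the point. It does not close the gap. Section 8.14.5 notes that some children with multiple islet antibodies develop thyroid autoimmunity as early as age 5 or 6, inside the untested window. An analysis rule can avoid false dating, but it cannot supply an order that was never assayed.

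**Conclusion.** The point holds in a limited form. Followed as written, section 8.14.5 leaves thyroid onset undated for children first found positive at step 5, mainly those diagnosed before 8, together with those whose islet and thyroid antibodies both arise between the age-8 test and diagnosis. For them hypothesis 4 cannot be answered, and thyroid timing for hypothesis 1 is known only as some time before diagnosis. Dating onset at step 5 would push the result towards islet-first, while leaving these children out is a selective loss of the fastest progressors.

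The figure of up to about 25 to 52 children is a rough upper guide. It rests on exponential diabetes onset, on the planned rather than the actual enrolment, and on thyroid prevalences not specific to children under 8, so the true number is probably lower. The point deserves correction because the direction of error is known and the remedy is small, but it does not bear on the primary outcomes.

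**What to change.** Extend the trigger in step 4 so that it covers a positive thyroid result from step 1, step 2 or step 5. Stored samples of children with diabetes would then be tested backwards by the procedure already planned for the others.

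Where stored serum is insufficient, treat thyroid onset as unknown before diagnosis: left-censored if there is no earlier negative thyroid test, interval-censored if there is one. State that the step 5 date is not used as onset in the test of hypothesis 4.

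The cost is several sequential assays per affected child, for probably fewer than 25 to 52 children diagnosed before 8 plus the uncounted later group. No new visits or blood draws are needed. Table 3 lists 0.1 mL of serum for a thyroid antibody test and shows repository serum from each visit. Section 10.2.2 warns that surplus blood volume is not expected, so sample availability should be checked first.
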